5.4.3.3 Congenital Anomalies/Birth Defects and Abortions

Any congenital anomaly/birth defect in a child born to a female patient exposed to study drug or the female partner of a male patient exposed to study drug should be classified as a serious adverse event, recorded on the Adverse Event eCRF, and reported to the Sponsor immediately (i.e., no more than 24 hours after learning of the event; see Section 5.4.2). Any abortion should be reported in the same fashion (as the Sponsor considers abortions to be medically significant).

5.5 FOLLOW-UP OF PATIENTS AFTER ADVERSE EVENTS

5.5.1 Investigator Follow-Up

The investigator should follow each adverse event until the event has resolved to baseline grade or better, the event is assessed as stable by the investigator, the patient is lost to follow-up, or the patient withdraws consent. Every effort should be made to follow all serious adverse events considered to be related to study drug or trial-related procedures until a final outcome can be reported.

During the study period, resolution of adverse events (with dates) should be documented on the Adverse Event eCRF and in the patient's medical record to facilitate source data verification.

All pregnancies reported during the study should be followed until pregnancy outcome.

5.5.2 Sponsor Follow-Up

For serious adverse events, adverse events of special interest, and pregnancies, the Sponsor or a designee may follow up by telephone, fax, email, and/or a monitoring visit to obtain additional case details and outcome information (e.g., from hospital discharge summaries, consultant reports, autopsy reports) in order to perform an independent medical assessment of the reported case.

5.6 ADVERSE EVENTS THAT OCCUR AFTER THE ADVERSE EVENT REPORTING PERIOD

The Sponsor should be notified if the investigator becomes aware of any serious adverse event that occurs after the end of the adverse event reporting period (defined as 4 weeks after the last dose of study drug; see Section 5.3.1), if the event is believed to be related to prior study drug treatment. These events should be reported through use of the Adverse Event eCRF. However, if the EDC system is not available, the investigator should report these events directly to the Sponsor or its designee, either by faxing or by scanning and emailing the Serious Adverse Event/Adverse Event of Special Interest Reporting Form using the fax number or email address provided to investigators.

5.7 EXPEDITED REPORTING TO HEALTH AUTHORITIES, INVESTIGATORS, INSTITUTIONAL REVIEW BOARDS, AND ETHICS COMMITTEES

The Sponsor will promptly evaluate all serious adverse events and adverse events of special interest against cumulative product experience to identify and expeditiously communicate possible new safety findings to investigators, IRBs, ECs, and applicable health authorities based on applicable legislation.

To determine reporting requirements for single adverse event cases, the Sponsor will assess the expectedness of these events using the following reference document:

- Fenebrutinib Investigator's Brochure

The Sponsor will compare the severity of each event and the cumulative event frequency reported for the study with the severity and frequency reported in the applicable reference document.

Reporting requirements will also be based on the investigator's assessment of causality and seriousness, with allowance for upgrading by the Sponsor as needed.

6. STATISTICAL CONSIDERATIONS AND ANALYSIS PLAN

The primary and secondary efficacy analyses will be based on a modified intent-to-treat (mITT) approach. All patients who received at least one dose of study drug will be included in the mITT population, with patients grouped according to the treatment assigned at randomization. Safety analyses will be conducted on the safety-evaluable population, defined as all patients who received at least one dose of study drug, with patients grouped according to the actual treatment received.

For each cohort, the final analysis of data from the 8-week, placebo-controlled period will be performed when the following two criteria have been met: 1) All patients in the cohort have either completed the Day 57 visit or discontinued from the placebo-controlled period prematurely and 2) all data from the placebo-controlled period in the cohort are in the database and have been cleaned and verified. Patients and study site personnel will remain blinded to the individual treatment assignment until after the study is completed (i.e., after all patients in both cohorts have either completed the safety follow-up period or discontinued early from the study), the database is locked, and the study analyses are final for both cohorts.

The focus of the trial is estimation and generation of hypotheses to be confirmed in future trials; therefore, Type I error control is not addressed.

6.1 DETERMINATION OF SAMPLE SIZE

6.1.1 Cohort 1: Pilot Assessment

The purpose of this cohort is to evaluate the efficacy of fenebrutinib at 200 mg PO BID compared with placebo in improving the UAS7. Point and interval estimates of the

change from baseline of the UAS7 within each treatment group as well as of the difference in change from baseline of the UAS7 between treatment groups will be presented.

The cohort will enroll approximately 45 patients. Patients will be randomized in a 2:1 ratio to receive treatment with either fenebrutinib or placebo. The sample size of approximately 30 patients in the fenebrutinib arm and 15 patients in the placebo arm provides approximately 80% power to detect an 11-point difference in the UAS7 change from baseline at Day 57 between treatment groups under the following assumptions:

- The absolute change from baseline at Day 57 is normally distributed with a standard deviation of 13.
- Two-sided alpha is 0.10.
- Dropout rate at Day 57 is 10%, leading to a 10% loss of information.

6.1.2 Cohort 2: Dose-Ranging Assessment

The purpose of this cohort is estimation and hypothesis generation regarding the dose-ranging effects of fenebrutinib compared with placebo in improving the UAS7. Point and interval estimates of the change from baseline of the UAS7 within each treatment group as well as of the difference in change from baseline of the UAS7 between treatment groups vs placebo will be presented.

The cohort will enroll approximately 120 patients. Patients will be randomly allocated in a 1:1:1:1 ratio to receive treatment with one of three dose levels of fenebrutinib or placebo. The sample size of approximately 30 in each arm provides approximately 90% power to detect an 11-point difference in the UAS7 change from baseline at Day 57 between treatment groups, under the following assumptions:

- The absolute change from baseline at Day 57 is normally distributed with a standard deviation of 13
- Two-sided alpha is 0.10
- Dropout rate at Day 57 is 10%, leading to a 10% loss of information.

The overall sample size may be adjusted depending on the outcome of a planned interim analysis for Cohort 1 (see Section 6.8), which will include an evaluation of these assumptions.

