3.3.5 Rationale for Pharmacokinetic Sample Collection Schedule

The sampling schedule is designed to assess multiple pre-dose (prior to study drug administration in clinic) plasma fenebrutinib concentrations, which will enable the estimation of systemic fenebrutinib exposures and subsequent exposure-response analyses, both of which may be reported separately. Results will be used to inform dosing regimens for future studies of fenebrutinib.

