4.3.2 Dosage, Administration, and Compliance of Fenebrutinib and Placebo

4.3.2.1 Fenebrutinib and Placebo Dose and Administration

For Cohort 1, the fenebrutinib dose level is 200 mg (4 tablets) BID (total of 8 tablets each day) with matching placebo (see Section 3.1). For Cohort 2, the fenebrutinib dose levels are 50 mg QD, 150 mg QD, and 200 mg BID, with matching placebos (see Table 3).

Patients in both cohorts will take fenebrutinib/placebo on Day 1 and ending on the Day 56 visit. Although *the Day 57 visit* is the last day of the study treatment period, no study drug for Study GS39684 will be given on *the Day 57 visit*. *If eligible, patients may enroll into the OLE Study GS40868 to receive their first open-label dose of fenebrutinib on Day 1 of the OLE or they will proceed and return for the safety follow-up visit 4 weeks after the last dose of study drug. For patients enrolling into the OLE, Day 1 of Study GS40868 may be the same day as the Day 57 visit in Study GS39684.*

For mandatory morning clinic visits (see Appendix 1 and Section 4.4.5), patients should be instructed that the morning dose of study drug will be taken in the clinic. On other clinic visit days, if the visit occurs in the morning, the patient should be instructed that the morning dose of study drug will be taken in the clinic.

Table 3 Fenebrutinib Dosing Regimen by Treatment Arm (Cohort 2)

| Fenebrutinib Dose Arm | Number of Tablets | |
|-----------------------|-----------------------------|------------------------|
| | Fenebrutinib (a.m./p.m.) | Placebo (a.m./p.m.) |
| 50 mg QD | 1/0 | 3/4 |
| 150 mg QD | 3/0 | 1/4 |
| 200 mg BID | 4/4 | 0/0 |
| Placebo | 0/0 | 4/4 |

BID=twice daily; QD=once daily.

Fenebrutinib or placebo may be taken orally with or without food, except on certain days (see [Appendix 1](#)), when the morning dose of oral study drug will be administered at the morning (mandatory) clinic visit while fasting. The dates and times of the most recent prior meal, last dose of oral study drug (prior to clinic visit), and timing of oral study drug administration in clinic should be recorded at each clinic visit. Patients should be instructed that a missed dose should not be taken with the next scheduled dose.

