6.4 EFFICACY ANALYSES

Statistical analysis will be conducted for each cohort separately. Statistical testing will be performed as a two-sided test with a statistical significance level of 0.10. No multiplicity adjustments will be performed to control overall Type I error, and positive tests will be viewed as hypothesis generating rather than confirmatory.

Continuous longitudinal efficacy endpoints will be analyzed using a mixed model for repeated measures (MMRM) and descriptive statistics as appropriate. An unstructured covariance pattern will be specified to model the within-subject errors. Parameters will be estimated with the use of restricted maximum likelihood, and the Kenward-Roger method will be used for calculating the denominator degrees of freedom. The MMRM method assumes that data are missing at random. That is, MMRM assumes that given the statistical model and given the observed values of the endpoint, missing data are independent of the unobserved values (O'Kelly and Ratitch 2014). High correlation between successive observations on a subject allows data from subjects who dropped out to make a contribution to estimation of the effects at the final timepoint.

All MMRM models will include country, treatment group, visit, and visit by treatment group interaction as covariates.

Time-to-event endpoints will be analyzed using a Cox proportional hazards model. Categorical endpoints will be analyzed using an appropriate statistical method, such as Cochran-Mantel-Haenszel test or Fisher's exact test.

Details of all statistical methods will be provided in the Data Analysis Plans (DAP).

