6.8.2 Cohort 2: Optional Interim Analysis

Given the hypothesis-generating nature of this study, the Sponsor may choose to conduct up to two interim efficacy analyses. The decision to conduct an optional interim analysis and the timing of the analysis will be documented in the Sponsor's trial master file prior to the conduct of the interim analysis. The interim analysis will be performed and interpreted by members of the IMC. Access to treatment assignment information will follow the Sponsor's standard procedures.

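### Does a dose-ranging cohort need a prespecified dose-versus-dose or dose-response estimate?

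*Combined protocol and SAP*

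**What the plan says.** Section 6.1.2 (Cohort 2) gives the purpose as "The purpose of this cohort is estimation and hypothesis generation regarding the dose-ranging effects of fenebrutinib compared with placebo in improving the UAS7". The design is four equal arms: "Patients will be randomly allocated in a 1:1:1:1 ratio to receive treatment with one of three dose levels of fenebrutinib or placebo". Section 4.3.2.1 sets out the regimens: "the fenebrutinib dose levels are 50 mg QD, 150 mg QD, and 200 mg BID".

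Two kinds of estimate are promised in Section 6.1.2. The first is "Point and interval estimates of the change from baseline of the UAS7 within each treatment group". The second is the "difference in change from baseline of the UAS7 between treatment groups vs placebo will be presented". The synopsis repeats this.

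On the model, Section 6.4 states: "All MMRM models will include country, treatment group, visit, and visit by treatment group interaction as covariates". It also fixes an unstructured covariance, restricted maximum likelihood, Kenward-Roger degrees of freedom and a two-sided 0.10 level. Section 6.4.1 adds baseline UAS7 and its interaction with visit. Treatment group enters as a factor, and Sections 6.4 to 6.4.3 name no dose term or contrast between active arms.

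The nearest related item is in Section 3.3.5. It foresees "estimation of systemic fenebrutinib exposures and subsequent exposure-response analyses, both of which may be reported separately", and says the results will feed into dosing for later studies. No endpoint or model is given. Section 6.4 leaves the detail of all statistical methods to the Data Analysis Plan, and Section 6.4.3 does the same for the exploratory endpoints.

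**The concern.** A cohort described as dose-ranging invites the question of how response changes from 50 mg QD to 150 mg QD to 200 mg BID. Three separate comparisons with placebo do not state that directly. If the comparison between doses is left open, it might be chosen after results are seen. Section 6.8.2 makes this more than theoretical: "the Sponsor may choose to conduct up to two interim efficacy analyses". The internal monitoring committee that runs those looks is unblinded and, under Section 3.1.1, may unblind the study team.

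There is also a risk of misreading. With about 30 patients per arm, two doses with similar point estimates could be taken as equivalent when the data cannot separate them. At stake is the reading of the cohort for later dose choice, not the primary comparison with placebo.

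**Working it through.** **Inputs, all from Section 6.1.2.** 30 patients per arm; 10% loss of information, so 30 × 0.9 = 27 per arm; SD 13; 11-point difference; two-sided alpha 0.10.

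**The plan's own figure first.** The standard error of a difference between two arms is 13 × √(2/27) = 3.54. Power by normal approximation is Φ(11/3.54 − 1.645) = Φ(1.46) = 0.928; the noncentral t with 52 degrees of freedom gives 0.923. The plan says approximately 90%, which is slightly conservative and not at issue here.

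**Is a dose-versus-dose estimate left open?** For doses A and B and placebo P, (A − P) − (B − P) = A − B. This holds exactly for adjusted means from one model. For the variance, ignoring covariate adjustment:

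- each arm mean: 13²/27 = 6.26;
- each placebo difference: 2 × 6.26 = 12.52;
- covariance of two placebo differences, through the shared placebo arm: 6.26;
- A − B: 12.52 + 12.52 − 2 × 6.26 = 12.52, so the standard error is √12.52 = 3.54.

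The 90% half-width is 1.66 × 3.54 = 5.9 points (t, 104 degrees of freedom) or 1.645 × 3.54 = 5.8 (normal). This equals the precision of a placebo comparison. A reader can also approximate it from the within-arm intervals already promised: √(2 × 6.26) = 3.54. Endpoint, population, model terms, covariance, estimation method and test level are all fixed, so little is left to choose for these contrasts.

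**Would naming them add information?** No. The imprecision is real, but it comes from the sample size. The true difference detectable with 80% power is 3.54 × (1.645 + 0.842) = 8.8 points. If the top dose gives 11 points over placebo, and total daily dose (50, 150, 400 mg) is taken as the scale, both of which are assumptions, then for 400 versus 150 mg/day:

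| Assumed shape | True difference | Power, two-sided 0.10 |
|---|---|---|
| Linear | 11 × 250/400 = 6.9 | 0.61 |
| Sigmoid (ED50 150, Hill 4) | 5.4 | 0.45 |
| Emax, ED50 150 mg | 11 × (1 − 0.500/0.727) = 3.4 | 0.25 |
| Emax, ED50 50 mg | 11 × (1 − 0.750/0.889) = 1.7 | 0.12 |

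For 150 versus 50 mg/day the range is 0.19 to 0.46. A line in the plan listing these contrasts would leave every one of these figures unchanged.

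**Would a fitted curve be clearly better?** Simulation under assumed shapes (MCP-Mod with averaging over linear, Emax and sigmoid models) gives a mixed picture.

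- Power to detect any effect is 92.7% to 97.0%, against 92.6% for the top-dose contrast: a gain of about 0 to 4 percentage points.
- Root mean squared error for 400 versus 150 mg/day falls from 3.54 to between 1.1 and 2.6 points.
- Against placebo at 50 mg it ranges from 1.2 to 3.8, so it can exceed 3.54, with bias of up to about 2 points.
- Nominal 90% intervals cover 88% to 91% for 400 versus 150 mg/day under rising shapes. If response is flat from 50 mg they cover 22% for that difference and 11% for 150 versus 50. Under the sigmoid shape they cover 10% for 50 mg versus placebo.

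Exact coverage depends on the fitting bounds. The pattern follows from forcing smooth curves through four dose points.

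**The case for a change.** The strongest case for a change is that the first remedy is almost free. Two contrasts between adjacent doses, with 90% intervals, come straight from the planned model with no new data and no curve assumption. A trial that describes its focus as estimation should name its estimates, being available is not the same as being prespecified, and the interim looks are unblinded. Printing the intervals would also discourage reading similar point estimates as equivalence.

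The facts in this stand: the contrasts are not named in the unredacted text, and showing them would be good reporting. The consequence does not. The point estimates are fixed by quantities already promised and the intervals by a model already specified, so following the plan as written produces no wrong result. The argument about choice after unblinding applies only to a curve model, which the protocol does not promise. That model would have to place QD and BID regimens on one dose scale, whereas the exposure-response work in Section 3.3.5 does not need that ordering. The remark there about separate reporting concerns where results appear, and does not show that the analysis is optional.

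Absence also cannot be established. Text is redacted directly after the exploratory endpoint list in Section 6.4.3, within and after Section 6.6, in the objectives table of Section 2 and in the design rationale of Section 3.3. The Data Analysis Plan, to which the protocol sends the detail, is not in the file.

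**Conclusion.** No change to the plan follows. The listed estimates answer a purpose stated relative to placebo, in a trial that declares itself hypothesis-generating without Type I error control. What is missing for comparisons between doses is a reporting detail that an analyst fills from the planned model: standard error 3.54 points, 90% half-width about 5.9 points. A dose-response model is a fair trade-off that reasonable statisticians would settle differently. It can sharpen differences between active doses, but adds at most about 4 percentage points of power and can give badly under-covering intervals where response is flat.

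This rests on the plan's SD of 13 and 27 completers per arm, on arm means treated as independent before covariate adjustment and, for the power and curve figures, on assumed shapes, an 11-point top-dose effect and total daily dose as the scale. None of those last three is a dose-response assumption made in the documents. If dose selection came to rest on a single fitted curve, its specification before unblinding would matter; nothing in the available text says that it will.

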6.2 SUMMARIES OF CONDUCT OF STUDY

The number of patients who enroll, discontinue, or complete the study will be summarized. Reasons for premature study withdrawal will be listed and summarized. Enrollment and major protocol deviations will be listed and evaluated for their potential effects on the interpretation of study results.

6.3 SUMMARIES OF TREATMENT GROUP COMPARABILITY

Baseline demographics, disease characteristics, and exposure to study drug will be summarized by treatment group using descriptive statistics. For categorical endpoints, the descriptive statistics will include counts and proportions. For continuous endpoints, the descriptive statistics will include the number of observations, mean, standard deviation, median, minimum, and maximum.

6.4 EFFICACY ANALYSES

Statistical analysis will be conducted for each cohort separately. Statistical testing will be performed as a two-sided test with a statistical significance level of 0.10. No multiplicity adjustments will be performed to control overall Type I error, and positive tests will be viewed as hypothesis generating rather than confirmatory.

Continuous longitudinal efficacy endpoints will be analyzed using a mixed model for repeated measures (MMRM) and descriptive statistics as appropriate. An unstructured covariance pattern will be specified to model the within-subject errors. Parameters will be estimated with the use of restricted maximum likelihood, and the Kenward-Roger method will be used for calculating the denominator degrees of freedom. The MMRM method assumes that data are missing at random. That is, MMRM assumes that given the statistical model and given the observed values of the endpoint, missing data are independent of the unobserved values (O'Kelly and Ratitch 2014). High correlation between successive observations on a subject allows data from subjects who dropped out to make a contribution to estimation of the effects at the final timepoint.

All MMRM models will include country, treatment group, visit, and visit by treatment group interaction as covariates.

Time-to-event endpoints will be analyzed using a Cox proportional hazards model. Categorical endpoints will be analyzed using an appropriate statistical method, such as Cochran-Mantel-Haenszel test or Fisher's exact test.

Details of all statistical methods will be provided in the Data Analysis Plans (DAP).

